We will assess the following variables during the baseline period: demographics, *a priori* defined covariates of interest, including comorbidities, concomitant medications, and risk factors for the outcomes, and cohort descriptors identified empirically from the most prevalent diagnoses, procedures, and prescriptions.

Study Sample Size

In a recent study of the MarketScan® Early View database, a total of 15212 erenumab-aooe users, 17239 users of other mAbs targeting the CGRP pathway, and 9242 users of onabotulinumtoxinA were identified from May 2018 through January 2020. Assuming a conservative 3-month growth rate of 15%, the expected number of new users during the study period (17 May 2018 – 31 May 2020) will be ~20 000 new users of erenumab-aooe, ~23 000 new users of other mAbs targeting the CGRP pathway, and ~13 000 new users of onabotulinumtoxinA.

Based on these sample size estimates, the 95% CIs for a cumulative incidence for stroke of 0.50% are (0.40%, 0.60%) for erenumab-aooe, (0.41%, 0.59%) for other mAbs targeting the CGRP pathway, and (0.38%, 0.62%) for onabotulinumtoxinA medication users. The 95% CIs and half-widths of the CIs were estimated across a range of cumulative incidence values, assuming varying population sizes, for all three cardiovascular outcomes of interest (hypertension, acute MI, and stroke).

If a comparative analysis is conducted (assuming 20 000 patients in the erenumab-aooe cohort and 20,000 patients in the comparator cohort, a background rate for stroke of 0.60 per 100 person-years (PYs), and an alpha-level of 0.05), a risk ratio of 1.46 would be detected with 80% power. Detectable risk ratios, assuming different population sizes and background rates, were estimated for acute MI and stroke.

• Data Analysis

Baseline characteristics, including the most prevalent diagnoses, procedures, and medication class prescriptions will be summarized for the four study cohorts. Descriptive statistics using mean and standard deviation or median and 25th/75th percentile estimates for continuous variables and number and percentages (n, %) for categorical variables will be used to examine patient characteristics.

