#### 6.3 Feasibility Considerations

In a recent internal Amgen study of the MarketScan® Early View database (Amgen Study 20200218), a total of 15212 erenumab-aooe users, 17239 users of other mAbs targeting the CGRP pathway, and 9242 users of onabotulinumtoxinA were identified from May 2018 through January 2020. In the same study, the rate of hypertension in new users of erenumab-aooe was 3.56 (95% confidence interval [CI]: 3.39, 3.73) per 10 PYs. In a separate study evaluating the rate of 19 vascular events in migraine patients, the rate of acute MI was 1.83 (95% CI: 1.78, 1.89) per 1000 PYs, the rate of ischemic stroke was 5.13 (95% CI: 5.04, 5.23) per 1000 PYs, and the rate of hemorrhagic stroke was 1.00 (95% CI: 0.95, 1.04) per 1000 PYs (Gill et al, 2020).

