#### Table 2. 95% CI Estimates and Half-widths for a Range of Cardiovascular Outcome Values, Based on a Sample Size of 20 000 Erenumab-aooe Users, 23 000 Users of Other mAbs Targeting the CGRP Pathway and 13 000 Onabotulinumtoxin A Users

	Erenumab-aooe N = 20 000		Other mAbs Targeting the CGRP Pathway N = 23 000		OnabotulinumtoxinsA N = 13 000	
CV Outcome (%)	95% CI	Half-width of Cl	95% CI	Half-width of Cl	95% CI	Half-width of Cl
0.20	0.14, 0.26	0.06	0.14, 0.26	0.06	0.12, 0.28	0.08
0.50	0.40, 0.60	0.10	0.41, 0.59	0.09	0.38, 0.62	0.12
1.00	0.86, 1.14	0.14	0.87, 1.13	0.13	0.83, 1.17	0.17
3.00	2.76, 3.24	0.24	2.78, 3.22	0.22	2.71, 3.29	0.29
5.00	4.70, 5.30	0.30	4.72, 5.28	0.28	4.63, 5.37	0.37
20.0	19.5, 20.6	0.55	19.5, 20.5	0.52	19.3, 20.7	0.69
30.0	29.4, 30.6	0.64	29.4, 30.6	0.59	29.2, 30.8	0.79

Abbreviations: CI: confidence interval; mAbs: monoclonal antibodies; CGRP: calcitonin gene-related peptide

Table 3 provides a range of detectable risk ratios for two outcomes of interest (acute MI and stroke), assuming 80% power, alpha-level of 0.05, and equal number of patients in each medication cohort, if a comparative analysis of the erenumab-aooe cohort to each comparator cohort (other mAbs targeting the CGRP pathway, selected SOC migraine preventive medications (anti-epileptics), or selected onabotulinumtoxinA ) were conducted. This table assumes a background rate of acute MI of 0.15 per 100 PYs and a background rate of stroke of 0.60 per 100 PYs (Gill et al, 2020).

 Table 3. Detectable Risk Ratios for Two Cardiovascular Outcomes

	Total Population in Each Medication Cohort						
Outcome	N = 13 000	N = 17 000	N = 20 000	N = 25 000			
Acute MI	2.10	1.94	1.85	1.75			
Stroke	1.58	1.51	1.46	1.41			

The estimates provided above are for informational purposes only. The final sample size for the study will change due to the criteria applied during the conduct of the protocol.

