### Decision to Proceed to Comparative Analyses

The decision to move forward with the comparative analysis for either the acute MI or the stroke outcome will be made after assessment of covariate balance across treatment groups (eg, based on an absolute standardized mean difference of > 0.10 for covariates included in the PS model, and adequate overlap in the PS across treatment arms), null findings for the final set of negative control outcomes (ie, posterior probability > 90% that the level of bias is less than 10% of the null), and sufficient sample size to detect a risk ratio of 2.0 or greater. For the relatively rate outcome of acute MI, a total of 15,000 patients in each comparator arm will be needed in order to detect a risk ratio of 2.0 or greater, assuming 80% power and a background rate of acute MI of 0.15 per 100 person-years. In contrast, for the outcome of stroke, 3,750 patients will be required in each treatment arm to detect a risk of 2.0 or greater, assuming 80% power and a background rate of stroke of 0.60 per 100 peson-years.

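### The stroke row of Table 3 and the abstract's 1.46 do not follow from their stated inputs, and the acute MI background rate differs without explanation from the figure quoted from the same study

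*Protocol*

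**What the plan says.** The abstract (Study Sample Size) works one example, "assuming 20 000 patients in the erenumab-aooe cohort and 20,000 patients in the comparator cohort", with "a background rate for stroke of 0.60 per 100 person-years (PYs), and an alpha-level of 0.05", and concludes that "a risk ratio of 1.46 would be detected with 80% power".

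Section 8.5 presents Table 3 "assuming 80% power, alpha-level of 0.05, and equal number of patients in each medication cohort". The background rates are "a background rate of acute MI of 0.15 per 100 PYs and a background rate of stroke of 0.60 per 100 PYs", both attributed to the cited vascular-event study in migraine patients. The printed detectable risk ratios are:

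| Outcome | N = 13,000 | N = 17,000 | N = 20,000 | N = 25,000 |
|---|---|---|---|---|
| Acute MI | 2.10 | 1.94 | 1.85 | 1.75 |
| Stroke | 1.58 | 1.51 | 1.46 | 1.41 |

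Section 6.3 reports from that same study that "the rate of acute MI was 1.83 (95% CI: 1.78, 1.89) per 1000 PYs", with ischemic stroke at 5.13 and hemorrhagic stroke at 1.00 per 1000 person-years.

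Section 8.7.2.4 (Decision to Proceed to Comparative Analyses) makes the ability to detect a risk ratio of 2.0 one of the conditions for running a comparison. At 80% power it asks for 15,000 patients per arm for acute MI at 0.15 per 100 person-years. For stroke at 0.60, it says that "3,750 patients will be required in each treatment arm".

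**The concern.** Both rows of Table 3 are presented under one set of assumptions, so one formula and one follow-up time should reproduce both. If one row needs a different power or a different background rate, a reader cannot tell what the study can detect for stroke, and the abstract repeats the affected figure.

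The acute MI rate raises a separate question of input. The stroke rate agrees with the cited study: 5.13 + 1.00 = 6.13 per 1000, or 0.613 per 100, against the 0.60 used. The acute MI rate does not: 1.83 per 1000 is 0.183 per 100, with interval 0.178 to 0.189, and the 0.15 used lies below that interval. The same 0.15 underlies the 15,000-per-arm requirement, so here the choice of input has an operational consequence.

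**Working it through.** **Inputs.** Alpha 0.05, 80% power, equal cohorts, N as in Table 3, and backgrounds of 0.15 and 0.60 per 100 person-years (Section 8.5). Two assumptions are mine because the Protocol does not state them: alpha is two-sided, and each patient contributes one person-year, so that risk equals rate.

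**Formula (arcsine, two proportions).** h(p) = 2·arcsin(√p), and power = Φ{[h(RR·p) − h(p)] / √(2/N) − 1.96}. For 80% power the standardized difference must equal 1.96 + 0.84 = 2.80.

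**Step 1: reproduce the acute MI row (p = 0.0015, 80% power).** The result is 2.097, 1.937, 1.853, 1.751 against the printed 2.10, 1.94, 1.85, 1.75. It matches to two decimals, which supports the formula and the one-person-year reading.

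**Step 2: reproduce the sample sizes for RR 2.0.** N per arm = 2·(2.80 / [h(2p) − h(p)])².
- Acute MI, 0.15%: about 15,200 (stated 15,000).
- Stroke, 0.60%: about 3,780 at 80% power (stated 3,750); at 90% power it would be about 5,060.

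Both stated sample sizes therefore fit 80% power at their stated rates.

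**Step 3: the stroke row (p = 0.006).**

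| | 13,000 | 17,000 | 20,000 | 25,000 |
|---|---|---|---|---|
| Printed | 1.58 | 1.51 | 1.46 | 1.41 |
| 0.60%, 80% power | 1.497 | 1.429 | 1.393 | 1.348 |
| 0.60%, 90% power | 1.584 | 1.503 | 1.460 | 1.408 |
| 0.45%, 80% power | 1.583 | 1.503 | 1.460 | 1.407 |
| Power at printed RR, 0.60% | 89.7% | 90.7% | 90.0% | 90.3% |

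The N = 20,000 cell by hand: h(0.00876) − h(0.006) = 0.18746 − 0.15507 = 0.03239. Dividing by √(2/20,000) = 0.01 gives 3.239, and Φ(3.239 − 1.96) = Φ(1.279) = 0.90.

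**Step 4: other formulas at N = 20,000, 0.60%, 80% power.** Pooled variance 1.394, continuity-corrected 1.403, log risk ratio 1.396, Schoenfeld 1.392, Freedman 1.396; one-sided alpha (pooled variance) 1.346. None reaches 1.46.

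**Step 5: could follow-up time explain it?** The stroke row fits 80% power if the risk is about 0.45%, which is 0.75 person-years at 0.60. At 0.75 person-years the acute MI risk is 0.1125%, and that row would read 2.30, 2.11, 2.01, 1.89 instead of what is printed. No single follow-up time fits both rows.

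**Step 6: acute MI at 0.183 per 100 person-years.** The detectable risk ratios at 80% power become about 1.98, 1.84, 1.76, 1.67 (pooled variance: 1.99, 1.85, 1.77, 1.68). N per arm for RR 2.0 becomes about 12,500 (pooled variance: about 12,800).

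**The case against.** The strongest reply is that little depends on the stroke row. Both departures are conservative, because the detectable risk ratios at the stated or quoted inputs are smaller than those printed. Section 8.5 calls its estimates informational, and cohort size is set by the database, not by recruitment. That stands, and it limits the seriousness. It does not make 1.46 a correct statement of what 80% power detects.

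Four stronger readings are tempting, and the Protocol does not support them.
- A reader might infer that Table 3 as a whole is wrong. The acute MI row reproduces exactly from its stated 0.15.
- A reader might infer that Table 3 determines which comparisons proceed. Section 8.7.2.4 uses its own sample sizes at RR 2.0. The smallest cohort in Table 3, 13,000, is more than three times 3,750, so stroke meets the size requirement whether 1.46 or 1.39 is printed.
- A reader might take these as the only power figures. Section 8.7.2.4 states 80% power for both outcomes.
- A reader might infer that the acute MI rate alone decides whether the onabotulinumtoxinA comparison qualifies, since about 13,000 users lies between 12,500 and 15,000. Allocation and formula matter as well: 20,000 erenumab users against 13,000 already give 81% power for RR 2.0 at 0.15% by arcsine, or 79% with pooled variance. The projection is also soft: 9,242 × 1.15² is about 12,200, below either threshold.

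It is also fair to say that 0.15 may be a deliberate or subgroup value from the cited study, which is not at hand. So this is an unexplained difference of input, not a proven error.

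**Conclusion.** The stroke row of Table 3 and the abstract's 1.46 are wrong as written. At 0.60 per 100 person-years, two-sided alpha 0.05 and 80% power the row is 1.50, 1.43, 1.39, 1.35. Which input slipped cannot be determined: 90% power at 0.60% and 80% power at about 0.45% fit the printed values equally well. The stroke result does not depend on the choice among standard formulas. It does assume one person-year per patient, which the exact match of the acute MI row supports. The practical effect is small: the study's sensitivity for stroke is understated, and no decision on the size of the stroke comparison changes.

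The acute MI point holds as an unexplained discrepancy between 0.15 and 0.183 per 100 person-years attributed to one study. It moves the per-arm requirement from 15,000 to roughly 12,500 to 12,800.

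**What to change.** - Restate the Table 3 stroke row as 1.50, 1.43, 1.39, 1.35 and the abstract figure as 1.39. Alternatively, keep the printed values and state the power or background rate that produced them.
- State the formula, the sidedness of alpha and the follow-up per patient once, for both rows.
- Reconcile the acute MI background with Section 6.3. Either give the reason for 0.15, or use 0.183 and restate the acute MI row as about 1.98, 1.84, 1.76, 1.67 and the Section 8.7.2.4 requirement as about 12,500 per arm (about 12,800 with pooled variance).

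The cost is one table row and one abstract figure, plus a sentence explaining 0.15. If 0.183 is adopted, a second row and one sample size also change. No analysis or data work is affected by the restatement itself.

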### 5. Amendments and Updates

None.

### 6. Rationale and Background

#### 6.1 Diseases and Therapeutic Area

Migraine is a common, disabling neurologic disease characterized by recurrent episodes of head pain associated with neurological, gastrointestinal, and/or autonomic symptoms (Kurth et al, 2009). The headache is usually located unilaterally, of pulsating quality and moderate to severe in intensity, and aggravated by physical activity (Dodick, 2018; Schürks et al, 2010). Approximately one-third of migraineurs experience migraine aura (MA), which is comprised of transient neurological symptoms (typically visual, sensory, and/or speech/language), prior to or at the onset of the migraine attack (Goadsby et al, 2002). The lifetime prevalence of migraine in the United States has been stable over time, ranging from 10% to 20% depending on the case definition and on the age and sex distribution of the study population (Lipton and Bigal, 2005; Bigal et al, 2004). The prevalence of migraine is three to four times higher in women than men (Lipton and

Bigal, 2005), and reaches a peak in the late 30s and early 40s (Sacco et al, 2014), with approximately 90% of all patients having their first migraine attack before the age of 50 years (Lipton and Bigal, 2005; Rasmussen et al, 1991).

There is growing evidence of a link between migraine and vascular events, but the biologic mechanisms remain unclear. This is because the pathophysiology of migraine is complex and incompletely understood, likely involving activation of the trigeminovascular system (Lantz et al, 2017; Silberstein, 2004; Ferrari et al, 2015) which is, in turn, caused by a dysfunction in the modulation of pain, sensory processing, and autonomic vascular control (Bigal et al, 2009; Goadsby, 1995; Bahra et al, 2001). Cortical spreading depression, which is characterized as a wave of synchronized depression of electrical activity followed by a decrease in cerebral blood flow, has been linked to the aura seen in many migraine patients (Kurth et al, 2012). In the epidemiology literature, four meta-analyses have suggested that migraine aura is a risk factor for ischemic stroke (Etminan et al, 2005; Schurks et al, 2009; Spector et al, 2010; Hu et al, 2017). With respect to other vascular events, including hemorrhagic stroke, transient ischemic attack, myocardial infarction, and unstable angina, there is also evidence of increased risk in migraine patients, when compared to patients without migraine (Sacco and Kurth, 2014).

Previous prophylactic treatment options for migraine have included anti-hypertensive drugs (eg, beta blockers and calcium channel blockers), anti-depressants (eg, tricyclics [TCAs], serotonin norepinephrine reuptake inhibitors [SNRIs], and selective serotonin reuptake inhibitors [SSRIs]), anti-epileptic medications (eg, topiramate), and botulinum toxins (indicated for the prevention of chronic migraine) (American Migraine Foundation, 2019; Estemalik et al, 2013; D'Amico and Tepper, 2008). All of these medications were originally developed for diseases other than migraine, but, more recently, two different classes of drugs blocking the calcitonin gene-related peptide (CGRP) pathway have been developed specifically for migraine: small molecule CGRP receptor antagonists (gepants) and monoclonal antibodies (mAbs), which either inhibit the canonical CGRP receptor or work by binding to the CGRP ligand (Deen et al, 2017).

The following four mAbs targeting the CGRP pathway have been approved for the prevention of migraine by the United States (US) Food and Drug Administration (FDA): erenumab-aooe (Aimovig®), fremanezumab-vfrm (Ajovy®), galcanezumab-gnlm (Emgality®), and eptinezumab-jjmr (Vyepti™). Erenumab-aooe was approved by the US FDA on 17 May 2018, followed by fremanezumab-vfrm on 14 September 2018,

galcanezumab-gnlm on 27 September 2018, and eptinezumab-jjmr on 21 February 2020.

#### 6.2 Rationale

CGRP is a neuropeptide that is expressed in the central and peripheral nervous systems and has been implicated in migraine pathophysiology. In addition, CGRP can mediate vasodilation (Russell et al, 2014) and, therefore, inhibition of the CGRP pathway might result in cardiovascular effects, such as increased blood pressure; however, vasodilatory pathways are redundant, and the relative importance of the CGRP pathway compared with the other vasodilatory pathways (eg, nitric oxide) has not been established. CGRP and its receptors are also found in blood vessels and in the heart (Favoni et al, 2019). Clinical trials evaluating CGRP mAbs for migraine prevention have shown no imbalance in CV adverse events, including hypertension, between active medication and placebo groups. Moreover, during the development of erenumab-aooe, a number of dedicated clinical and nonclinical studies were conducted to address a theoretical cardiovascular risk, and collectively these studies support the cardiovascular safety of erenumab-aooe (Kudrow et al, 2020).

During the fourth quarter of 2019, the FDA identified hypertension as a potential adverse drug reaction (ADR) for erenumab-aooe. On 30 April 2020, new onset hypertension and exacerbation of existing hypertension were added to the Warning and Precautions section of the USPI for erenumab-aooe. In addition, because the phase 2 and 3 clinical trials for erenumab-aooe had a limited number of subjects (0.5%) enrolled with preexisting cardiovascular (CV) disease (Dodick et al, 2018; Goadsby et al, 2017, Tepper et al, 2017), use of erenumab-aooe in patients with major CV disease (including acute myocardial infarction [MI] and stroke) is classified as missing information in the Core Risk Management Plan for erenumab-aooe.

In this study, the risk of hypertension, acute MI, and stroke will be estimated in the following four new user cohorts: erenumab-aooe, other mAbs targeting the CGRP pathway, select standard of care (SOC) migraine preventive medications (anti-epileptics), and onabotulinumtoxinA. Also, if appropriate based on comparability analyses, the relative risk (RR) of acute MI and stroke will be separately estimated for the following three comparisons: (1) erenumab-aooe vs. other mAbs

targeting the CGRP pathway, (2) erenumab-aooe vs. select SOC migraine preventive medications (anti-epileptics), and (3) erenumab-aooe vs. onabotulinumtoxinA.

#### 6.3 Feasibility Considerations

In a recent internal Amgen study of the MarketScan® Early View database (Amgen Study 20200218), a total of 15212 erenumab-aooe users, 17239 users of other mAbs targeting the CGRP pathway, and 9242 users of onabotulinumtoxinA were identified from May 2018 through January 2020. In the same study, the rate of hypertension in new users of erenumab-aooe was 3.56 (95% confidence interval [CI]: 3.39, 3.73) per 10 PYs. In a separate study evaluating the rate of 19 vascular events in migraine patients, the rate of acute MI was 1.83 (95% CI: 1.78, 1.89) per 1000 PYs, the rate of ischemic stroke was 5.13 (95% CI: 5.04, 5.23) per 1000 PYs, and the rate of hemorrhagic stroke was 1.00 (95% CI: 0.95, 1.04) per 1000 PYs (Gill et al, 2020).

### 6.4 Statistical Inference

We will: (1) estimate the cumulative incidence (95% confidence interval [CI]) of hypertension, acute MI, and stroke (ischemic and hemorrhagic) in initiators of erenumab-aooe, other mAbs targeting the CGRP pathway, select SOC migraine preventive medications (anti-epileptics), and onabotulinumtoxinA; and, (2) if the cohorts are comparable, we will separately evaluate the null hypothesis of no association between erenumab-aooe versus each of the other new user cohorts on the cumulative incidence (ie, risk) of acute MI and stroke.

#### 7. Research Question and Objectives

#### 7.1 Primary

This study protocol will address the following objectives:

- (1) To describe baseline characteristics of four cohorts of migraine patients initiating a migraine preventive treatment: erenumab-aooe, other mAbs targeting the CGRP pathway, selected SOC migraine preventive medications (anti-epileptics), and onabotulinumtoxinA.
- (2) To estimate the cumulative incidence of hypertension, acute MI, and stroke in migraine patients treated with erenumab-aooe, other mAbs targeting the CGRP pathway, selected SOC migraine preventive medications (anti-epileptics), and onabotulinumtoxinA.
- (3) To assess comparability, as described in Section 8.7.2.4, of migraine patients treated with erenumab-aooe to migraine patients treated with (1) other mAbs targeting the CGRP pathway, (2) selected SOC migraine preventive medications (anti-epileptics), and 3) onabotulinumtoxinA, with respect to baseline confounders and risk factors for cardiovascular disease. Comparability between

medication cohorts will be evaluated with propensity score analyses, evaluation of the standardized mean difference for all variables included in the propensity score model, and negative control outcome analyses.

(4) [GATED ANALYSES] If the cohorts are comparable, separately compare the cumulative incidence of acute MI and stroke among migraine patients treated with erenumab-aooe to migraine patients treated with (1) other mAbs targeting the CGRP pathway, (2) selected SOC migraine preventive medications (antiepileptics), and 3) onabotulinumtoxinA.

### 8. Research Methods

### 8.1 Study Design

This study will utilize an observational retrospective cohort study design, using secondary data from the MarketScan® Commercial and Medicare Supplemental medical claims database. The strength of the cohort study design is the ability to study multiple outcomes in a single study. In this study, the following events that occur during the follow-up period will be evaluated: hypertension, stroke, and acute MI. All outcomes will be identified using International Classification of Diseases, 10th Revision, Clinical Modification (ICD-10-CM) diagnosis codes. New user cohorts for erenumab-acoe, other mAbs targeting the CGRP pathway (galcanezumab-gnlm, fremanezumab-vfrm, eptinezumab-jjmr), selected SOC migraine preventive medications (anti-epileptics: topiramate, valproic acid, divalproex sodium) which are approved by the FDA for the prevention of migraine, and , onabotulinumtoxinA, which is also approved by the FDA for the prevention of migraine, will be created based on National Drug Code (NDC) and Healthcare Common Procedure Coding System (HCPCS) codes that occur during the study period. To evaluate the burden of disease, the cumulative incidence (ie, risk) of each outcome, across all four new user cohorts, will be estimated. For the outcomes of acute MI and stroke, the three causal contrasts of interest are the following:

- (1) Erenumab-aooe vs other mAbs targeting the CGRP pathway
- (2) Erenumab-aooe vs select SOC migraine preventive medications (anti-epileptics)
- (3) Erenumab-aooe vs. onabotulinumtoxinA

The measure of effect that will be estimated for the comparative analyses is the RR.

